(0.8 mT) magnet to protect against stray external magnetic fields (pictured below). The filling pressure of the gas allows 1 L of useable gas when released. The container is then shipped to the imaging center where it is transferred to the tedlar bags and administered to the subject. This system has been previously tested successfully in Europe and Australia. (21, 22)

Hypothesis to be Tested

The purpose of this study is to further develop the technique of rapid hyperpolarized helium-3 MRI for use in infants, and perform a pilot study in infants who are healthy and infants with CF, BPD, and asthma.

Study Design: Biomedical

1. Will controls be used? No.

2. What is the study design?

Pilot.

3. Does the study involve a placebo?

No.

Human Participants

Ages: 1 month -65 years old

Sex: Both

Race: All

Subjects- see below

- 1. Provide target # of subjects (at all sites) needed to complete protocol.** 110.
- 2. Describe expected rate of screen failure/ dropouts/withdrawals from all sites.** 10%.

- 3. How many subjects will be enrolled at all sites?** 121.
4. How many subjects will sign a consent form under this UVa protocol? 121.
- 5. Provide an estimated time line for the study.** We expect to complete this study in 5 years.

Inclusion/Exclusion Criteria

1. List the criteria for inclusion

We confirm that this protocol includes two arms: 1) one that enrolls adults and children age >1 month to fine tune the details of the MRI sequence acquisitions and 2) a pilot study that enrolls infants and young children age >1 month with either healthy or diseased lungs. Some of the subjects in arm 2 may be on a ventilator and ready to wean.

MRI sequence development (n=60):

Healthy subjects and patients with CF, BPD, asthma, COPD, a history of smoking or other lung diseases will be used in the development of the rapid imaging techniques. These subjects will be age 1 months to 65 years old. Healthy subjects can have no history of chronic respiratory disease. The subjects with CF, asthma, or BPD must have a physician diagnosis of their respective disease.

Pilot Study (n=50):

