- A urine pregnancy test will be done for women of childbearing potential, who report the possibility that they might be pregnant.
- If needed, a practice bag filled with room air will be given to the subject as a teaching tool to teach the subjects the breathing technique used during the administration of hyperpolarized helium gas.
- Before and after MR imaging, a physical exam, spirometry (if subject able to perform test), and a baseline %PO₂ will be performed.
- During the MR imaging procedure, the subject's heart rate and blood oxygen saturation will be monitored using an MR compatible pulse oximeter when possible.
- Once positioned in the MR scanner, the free breathing MR imaging will be performed.
- Then, the hyperpolarized helium 3 imaging will be performed.
 - Subjects who are infants will be bundled or held to restrain motion while in the MRI scanner
 - Infants will be placed in the MR coil such that their head is supported in a neutral position. Imaging occurs very quickly so the total time the subject is expected to be in the scanner is less than 15 minutes.
 - For infants with BPD, a physician from the research team will be present at all imaging sessions to monitor the subject. Imaging will be terminated if the physician feels the baby is being unusually stressed in any way.
 - Imaging will be terminated and oxygen given if the subject's pO₂ on pulse oximetry drops by 10% or more or if there is a sustained low heart rate over one minute of less than 100 bpm heart rate. We have experience with MR imaging of young infants for clinical brain MRI and most infants tolerate imaging of the brain MRI well. We expect infants to tolerate the lung imaging well particularly since the duration of imaging will be less than brain MRI.
 - If the subject is not on a ventilator, the subject will inhale the hyperpolarized gas which may be mixed with medical grade nitrogen through a small plastic tube connected to a plastic bag containing the hyperpolarized gas mixture or through a face mask or other gas delivery device. If the subject is on a ventilator the hyperpolarized gas mixture will be introduced into the ventilator circuit just before the endotracheal or tracheostomy tube.
 - Rapid MR imaging will be performed during inhalation/exhalation and/or breath-hold. Depending upon the availability of gas and the quality of images obtained, the helium-3 inhalation and MR imaging may be repeated.

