 - Oxygen by nasal cannula or mask may be administered immediately before and after gas inhalation.
 - The dedicated transmit/receive MR coils used for the gas imaging is an investigational, non-FDA approved device. However, the manufacturer considers it a non-significant risk device. In addition, non-standard MR pulse sequences are used for hyperpolarized gas imaging. In general these sequences require much lower power depositions than conventional MR imaging and therefore include no significant risk.

- Conventional proton images of the thorax may also be obtained to define the lung boundaries for subsequent image analysis.
- May use an inline flow meter to measure the airway flow and gas volumes during dosing with practice bags outside of the scanner and with dosing bags while in the scanner.
- The total time of the MR image acquisition is limited typically less than 20 seconds. The total study visit duration is expected to be 3-4 hours.

Subjects will be contacted from 1-5 days via telephone or email after imaging to assess for side effects and adverse events.

NOTE: Gadolinium will not be used for this study.

2. List the procedures, in bullet form, that will be done for RESEARCH PURPOSES as stipulated in this protocol.

All procedures are being done for the research study.

3. Do you confirm that, except for blood draws through a peripheral site, that all invasive procedures will be performed by a licensed health care provider under the supervision of an MD? Yes.

4. Will you be using data/specimens in this study that were collected previously, with the use of a research consent form, from another research study? No.

5. Will any of the procedures listed in item # 2 have the potential to identify an incidental finding? This includes ALL procedures, assessments and evaluations that are being done for RESEARCH PURPOSES that may or may not be considered investigational. Yes.

► IF YES, check one of the following two options:

The examination(s) utilize(s) the same techniques, equipment, etc., that would be used if the subject were to have the examination(s) performed for clinical care. **There exists the potential for the discovery of clinically significant incidental findings.** (limited physical exam, spirometry, urine pregnancy test, if needed, vital signs)

- The PI takes full responsibility for the identification of incidental findings:

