2.1 What risks are expected due to the intervention in this protocol?

Expected Risks related to study participation.	Frequency

Risk of Inhaling Hyperpolarized Helium 3 gas	

The most common respiratory related symptoms include sore, dry or scratchy throat; tickle in throat; and coughAdditional non-respiratory related symptoms have also occurred and include headache and lightheadedness	 Occurs frequently,  Occurs infrequently  Occurs rarely  Frequency unknown

Other respiratory related symptoms include wheezing, chest tightness or chest pain and a decrease >10% in %PO2	 Occurs frequently,  Occurs infrequently  Occurs rarely  Frequency unknown

A small amount of the element rubidium is used to hyperpolarize the helium gas. The quantity used is less than 1/1000 of the amount that would poison a rat, though it is in a chemical form that a small droplet would cause a heat releasing reaction.	 Has never occurred

Risk of Magnetic Resonance Imaging	

If you have metal shards or clips in your body, they may interfere with the magnetic field and give burns	 Occurs frequently,  Occurs infrequently  Occurs rarely  Frequency unknown

Claustrophobia: It is possible to feel a sensation of being confined or caged when in the MRI machine.	 Occurs frequently  Occurs infrequently  Occurs rarely  Frequency unknown

Risks related to the investigational coil	

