- For MRI scanning: Participants need to complete the standard MR questionnaire that is also used at the clinical sites to screen the individuals ineligible for MRI scanning: This screens for metallic foreign bodies, inner ear implants, pacemakers, claustrophobia, etc.

- For MR scanning with inhaled hyperpolarized helium-3. Individuals whose body habitus does not allow the person to fit in the special vest coils for imaging at the MR frequency of hyperpolarized helium-3 are excluded. In case of doubt the vest coil will be fitted around the participant outside the scanner to determine eligibility.
- Follow-up for adverse events is performed within 1 to 5 days post imaging by telephone or email contact.
- All NICU infants, whether or not they are on a ventilator, will be transported to MRI per standard clinical care procedures and NICU personnel will remain with the infant during imaging per standard care.

2.3 Under what criteria would an INDIVIDUAL SUBJECT'S study treatment or study participation be stopped or modified

At subject, PI or sponsor's request

2.4 Under what criteria would THE ENTIRE STUDY need to be stopped.

Per IRB, PI, DSMB, or sponsor discretion

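### The rule for stopping imaging uses a heart rate below 100 bpm with no age limit, so read literally it stops most resting adults; it should be limited to infants

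*Combined protocol and SAP*

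**What the plan says.** The rule is in Biomedical Research, item 1 (What will be done in this protocol?), in the list under helium imaging. One mandatory sentence has two triggers: a fall of 10% or more in the subject's oxygen reading on pulse oximetry, or a "sustained low heart rate over one minute of less than 100 bpm heart rate". Either one ends imaging and calls for oxygen. No age or study arm is named.

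Earlier in the same item, for all subjects, "heart rate and blood oxygen saturation will be monitored using an MR compatible pulse oximeter when possible".

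Inclusion/Exclusion Criteria, item 1, says of the development arm: "These subjects will be age 1 months to 65 years old". The same item states that this arm takes adults as well as children.

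Two pieces of nearby text concern infants:
- The sub-bullet just before the rule covers infants with BPD: "Imaging will be terminated if the physician feels the baby is being unusually stressed in any way".
- The rule's own bullet goes on to discuss young infants having brain MRI and adds: "We expect infants to tolerate the lung imaging well".

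The Data and Safety Monitoring Plan, section 2.3, gives the criterion for stopping an individual subject as "At subject, PI or sponsor's request". It adds no heart-rate limit for any age.

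**The concern.** The two triggers are of different kinds. The oxygen trigger is a change from the subject's own level, so it makes sense at any age. The heart-rate trigger is an absolute level. A sustained rate under 100 bpm may be a warning sign in an infant, but it is an ordinary resting pulse in an adult. An adult can therefore meet the criterion on entering the scanner, with no reaction to the gas at all.

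Because the rule is mandatory, staff must either stop such scans or set the rule aside by judgement. They would probably do the second. On the literal text, continuing would then be an unapproved departure from procedure, which section 1.4 of the monitoring plan defines as a protocol violation. The reporting table in section 3.7 sends protocol violations to the sponsor within 7 calendar days. A safety rule that has to be ignored routinely in one age group is also hard to audit in the others.

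**Working it through.** There is no sample-size, power or error-rate figure to reproduce. The check has three parts.

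**1. Can the criterion be met in an adult session?** It needs one minute of monitored heart rate. The Pharmacy appendix, item 5, expects imaging sessions of 30 to 60 minutes, and monitoring is planned for every subject where possible. One minute is available even though each acquisition is short.

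**2. What share of adults would meet it?** The documents give no adult heart rates, so the means and SDs below are assumptions. Treat a person's sustained resting rate as normal with mean μ and standard deviation σ. Then

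P(rate < 100) = Φ((100 − μ)/σ)

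| Assumed μ, σ (bpm) | (100 − μ)/σ | Share below 100 bpm |
|---|---|---|
| 65, 10 | 3.50 | 100.0% |
| 75, 12 | 2.08 | 98.1% |
| 80, 12 | 1.67 | 95.2% |
| 85, 15 | 1.00 | 84.1% |
| 90, 15 | 0.67 | 74.8% |

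The range is about 75% to 100%. Even with μ = 95 and σ = 15 the share is 63.1%. For any symmetric distribution with a mean below 100 bpm it exceeds half, so the statement that most resting adults qualify does not depend on the particular values. This cannot be turned into a number of subjects, because the adult share of the 60 is not stated.

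**3. What does each reading of the sentence imply?**

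| Reading | Heart-rate trigger | Oxygen trigger |
|---|---|---|
| Literal: both triggers for every subject | Stops most resting adults | Covers every subject |
| Whole sentence for infants only | Works | Would not reach older subjects |
| Oxygen for everyone, heart rate for infants | Works | Covers every subject |

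The third reading works on both counts. It also fits section 2.1 of the monitoring plan, which lists "wheezing, chest tightness or chest pain and a decrease >10% in %PO2" as a rare risk without restricting it by age. The text does not state this reading.

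**The case against.** The strongest reply is that context settles the matter. Three sub-bullets about infants come immediately before the rule, and the sentences after it in the same bullet are about infants. The trigger is a low heart rate, and 100 bpm counts as low only in an infant. The infant sub-bullets themselves also call the infant the subject, so that word alone does not prove that adults are included. All of this stands as evidence of intent. It does not supply the missing limit. The preceding sub-bullets name infants at the outset, this one does not, and the next one, on gas delivery, is not confined to infants.

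The second reply is that the consequence is small and mostly on the safe side: a scan ends early and oxygen is given. Monitoring is only done where possible, and acquisition typically takes under 20 seconds. In addition, "Oxygen by nasal cannula or mask may be administered immediately before and after gas inhalation". Oxygen saturation is also checked before and after inhalation (section 2.2). This stands, and it is why the point is minor.

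A reader might go further and infer that adults have no numeric limit for desaturation. The documents do not support that. The oxygen trigger refers to the subject's reading and nothing in its own words confines it to infants. The gap appears only if the whole sentence is read as infant-only. That reading cannot be combined with the literal one used for heart rate, since each removes the other's problem.

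**Conclusion.** The defect is real but small. As written, a mandatory stopping rule applies an absolute threshold of 100 bpm to subjects up to 65 years old, and about 75% to 100% of resting adults would meet it. The percentages rest on assumed normal distributions; the conclusion that most adults qualify needs only a roughly symmetric distribution with a mean below 100 bpm.

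The likely intent was infants only. It would be wrong to conclude that the team would in fact stop adult scans, that the development arm would lose a countable number of subjects, or that older subjects lack a desaturation limit. The documents establish none of these. What they establish is a rule whose literal scope is wrong for adults. The correction concerns safety conduct and touches no endpoint, sample size or analysis.

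**What to change.** Leave the 10% oxygen trigger in place for any subject, as its words already provide. Move the heart-rate trigger to its own sentence, for example:

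*In infants up to [age], imaging will also be terminated and oxygen given for a sustained heart rate below 100 bpm over one minute.*

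The investigator should set the age. The documents offer two candidates: the note in the opening statement of purpose puts under one year of age beside infants, while the pilot study enrols infants of 1 to 24 months. Nothing in the text shows which one suits a 100 bpm limit. Whether older children and adults need a heart-rate limit of their own, and at what value, is also for the investigator; the documents give no basis for a number.

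The cost is a one-sentence protocol amendment, with no added procedures, subjects or analyses.

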1.1 How will you define adverse events (AE) for this study?

An adverse event will be considered any undesirable sign, symptom or medical or psychological condition **even if the event is not considered to be related** to the investigational drug/device/intervention. Medical condition/diseases present before starting the investigational drug/intervention will be considered adverse events only if they worsen after starting study treatment/intervention. An adverse event is also any undesirable and unintended effect of research occurring in human subjects as a result of the collection of identifiable private information under the research. Adverse events also include any problems associated with the use of an investigational device that adversely affects the rights, safety or welfare of subject s.

1.2 How will you define serious adverse events?

A serious adverse event will be considered any undesirable sign, symptom, or medical condition which is fatal, is life-threatening, requires or prolongs inpatient hospitalization, results in persistent or significant disability/incapacity, constitutes a congenital anomaly or birth defect, is medically significant and which the investigator regards as serious based on appropriate medical judgment. An important medical event is any AE that may not result in

death, be life-threatening, or require hospitalization but may be considered an SAE when, based upon appropriate medical judgment, it may jeopardize the patient and may require medical or surgical intervention to prevent one of the outcomes listed in the definitions of SAEs.

1.3 What is the definition of an unanticipated problem?

Do not change this answer

An unanticipated problem is any event, experience that meets ALL 3 criteria below:

- Is unexpected in terms of nature, severity or frequency given the research procedures that are described in the protocol-related documents AND in the characteristics of the subject population being studied
- Related or possibly related to participation in research. This means that there is a reasonable possibility that the incident may have been caused by the procedures involved in the research study.
- The incident suggests that the research placed the subject or others at greater risk of harm than was previously known or recognized OR results in actual harm to the subject or others

1.4 What are the definitions of a protocol violation and/or noncompliance?

Do not change this answer

A **protocol violation** is defined as any change, deviation, or departure from the study design or procedures of research project that is NOT approved by the IRB-HSR prior to its initiation or implementation. Protocol violations may be major or minor violations.

Noncompliance can be a protocol violation OR deviation from standard operating procedures, Good Clinical Practices (GCPs), federal, state or local regulations. Noncompliance may be serious or continuing.

Additional Information: see the IRB-HSR website at

http://www.virginia.edu/vpr/irb/HSR_docs/Forms/Protocol_Violations_%20Enrollment_Exceptions_Instructions.doc

1.5 If pregnancy occurs how will this information be managed?

X Unanticipated Problems- will follow Unanticipated Problem recording and reporting procedures outlined in section 3.

1.6 What is the definition of a Protocol Enrollment Exception?

X Protocol has a sponsor outside of UVa. An enrollment exception is the sponsor's prospective approval for the enrollment of a research subject that fails to meet current IRB-HSR approved protocol inclusion criteria, or falls under protocol exclusion criteria. Enrollment exceptions only apply to a single individual. Such a request should be rare and justified in terms of serving the best interests of the potential study participant.

1.7 What is the definition of a data breach?

Do not change this answer

A data breach is defined in the HITECH Act (43 USC 17932) as an unauthorized acquisition, access, or use of protected health information (PHI) that compromises the security or privacy of such information.

Additional Information may be found on the IRB-HSR Website: [Data Breach](#)

2. Identified risks and plans to minimize risk

2.1 What risks are expected due to the intervention in this protocol?

Expected Risks related to study participation.	Frequency

Risk of Inhaling Hyperpolarized Helium 3 gas	

The most common respiratory related symptoms include sore, dry or scratchy throat; tickle in throat; and coughAdditional non-respiratory related symptoms have also occurred and include headache and lightheadedness	 Occurs frequently,  Occurs infrequently  Occurs rarely  Frequency unknown

Other respiratory related symptoms include wheezing, chest tightness or chest pain and a decrease >10% in %PO2	 Occurs frequently,  Occurs infrequently  Occurs rarely  Frequency unknown

A small amount of the element rubidium is used to hyperpolarize the helium gas. The quantity used is less than 1/1000 of the amount that would poison a rat, though it is in a chemical form that a small droplet would cause a heat releasing reaction.	 Has never occurred

Risk of Magnetic Resonance Imaging	

If you have metal shards or clips in your body, they may interfere with the magnetic field and give burns	 Occurs frequently,  Occurs infrequently  Occurs rarely  Frequency unknown

Claustrophobia: It is possible to feel a sensation of being confined or caged when in the MRI machine.	 Occurs frequently  Occurs infrequently  Occurs rarely  Frequency unknown

Risks related to the investigational coil	


 This coil, which is necessary to obtain the MR images of the lungs with the hyperpolarized gas, transmits and receives radio waves at much lower power than used with most standard MRI techniques. The coil is considered by the manufacturer a non-significant risk device, but it has not been approved by the FDA. 	 Occurs frequently,  Occurs infrequently  Occurs rarely  Frequency unknown
--	--

Risk related to Spirometry	

 Since spirometry requires blowing hard several times, the subject may cough or feel short of breath during or after the test. 	 Occurs frequently,  Occurs infrequently  Occurs rarely  Frequency unknown

Risk to a fetus	

 For females: At present, the safety of hyperpolarized gas to a fetus has not been established. If you are pregnant or nursing you may not participate in this study. 	 Occurs frequently,  Occurs infrequently  Occurs rarely  Frequency unknown

 For males: You should not father a baby while you are in this study or for one month after your participation in the study ends 	 Occurs frequently,  Occurs infrequently  Occurs rarely  Frequency unknown

Risk of Transport	

 Risk of dislodgement of the endotracheal tube Unplanned extubation 	 Occurs frequently,  Occurs infrequently  Occurs rarely  Frequency unknown

2.2 List by bullet format a summary of safety tests/procedures/observations to be performed that will minimize risks to participants:

- Medical History questionnaire
- Pre and post inhalation measurement of spirometry
- Pre and post inhalation measurement of oxygen saturation monitoring (pulsoximetry)
- For MRI scanning: Participants need to complete the standard MR questionnaire that is also used at the clinical sites to screen the individuals ineligible for MRI scanning: This screens for metallic foreign bodies, inner ear implants, pacemakers, claustrophobia, etc.

- For MR scanning with inhaled hyperpolarized helium-3. Individuals whose body habitus does not allow the person to fit in the special vest coils for imaging at the MR frequency of hyperpolarized helium-3 are excluded. In case of doubt the vest coil will be fitted around the participant outside the scanner to determine eligibility.
- Follow-up for adverse events is performed within 1 to 5 days post imaging by telephone or email contact.
- All NICU infants, whether or not they are on a ventilator, will be transported to MRI per standard clinical care procedures and NICU personnel will remain with the infant during imaging per standard care.

2.3 Under what criteria would an INDIVIDUAL SUBJECT'S study treatment or study participation be stopped or modified

At subject, PI or sponsor's request

2.4 Under what criteria would THE ENTIRE STUDY need to be stopped.

Per IRB, PI, DSMB, or sponsor discretion

